The STOMP behavioral intervention consists of 12 intervention sessions (6 group and 6 individual sessions). The sessions will be completed over a period of 12-16 weeks from enrollment. The first intervention session will be a group session for all participants followed by individual and then alternating group and individual sessions for the rest of the intervention. The intervention group will utilize a study manual on pain management in which they will use with each session.

Group intervention Sessions

A total of 6 group sessions will be conducted over a period of 12-16 weeks from study enrollment date. These sessions will be led by a peer. A peer is an HIV-infected patient of the UAB or UNC clinics living with chronic pain and is a successful self-manager of his/her chronic pain. Peers will receive training that will include being a participant in all one-on-one sessions, and additional training to co-facilitate the six group sessions with the interventionist. Prior to the beginning of the first group session, participants will sign an Agreement of Confidentiality.

Participants will receive a reminder call/text approximately 48 hours before the group session to remind them of the upcoming session by the peer interventionist. If the participants cannot be reached on first contact, the peer interventionist will conduct up to three reminder calls or texts before the group session. Participants will also be notified of the upcoming group sessions at the end of each one-on-one intervention. Group sessions will be conducted in designated clinics at UAB and UNC. A sign-in sheet will be used to document attendance. Session notes will be used to document any major issues presented or any anecdotal nuances identified. The date, start time and end time of the

session will also be documented. Participants will complete an anonymous session feedback form at the end of each session. Each session will be audio recorded and transcribed later using a third party.

Individual Intervention Sessions

A total of 6 individual sessions will be conducted over a period of 12-16 weeks from study enrollment date.

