Participants assigned to intervention arm, peers and interventionists of the study will be interviewed at mid-point of the study and end of the study to provide their feedback on the STOMP intervention. These interviews will be audio-recorded and later transcribed using third party. Participants will be compensated \$50 for each of the qualitative interviews.

e) COMPARISON CONDITION

The comparison group will receive “treatment as usual” as described above. The comparison group will also be provided with the intervention manual, however, no additional treatment will be provided to participants allocated to the control group.

Assessments

The comparison group participants will complete the post-intervention (0-month) follow-up at the same timing of the intervention group (12 - 16 weeks) after the 1st intervention session., and then will complete the outcome assessments (3,6,9,12) as the intervention group as described above including the baseline and the 12-month viral load assessments, and the important medical event screening at post-intervention. We will continue to conduct assessments every six months until the end of the study for all participants who complete the baseline assessment by the beginning of Year 3. Participants who completed the baseline assessment by April 30, 2021 will continue to

receive outcome assessments until April 2023 for a maximum of 41 months or 3 years. These assessments may be conducted by phone, if necessary, or in person.

We will also investigate the intervention's impact on use of prescribed and non-prescribed opioids. Study staff will ask at each outcome assessment (3,6,9,12) the name of the participants' pharmacies along with the list of their current medications and dosage. Study staff will print out the medication lists and review it against the Opioid Medication Resource to identify the prescribed opioids. With written consent and a signed release of information from participants, a study staff member will contact the participants' pharmacy (or pharmacies) at the 12-month assessment to verify the self-reported information provided by the participants in the prior assessments. The data will be added into an excel spreadsheet for collection and analysis. Participants will receive up to 3 reminder calls at about a week and 48 hours prior to the next outcome assessment.

f) PEER INTERVENTIONISTS

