Sample Size Calculation. Our primary outcome is the BPI-Total score as described above. Given that 20 participants progress through the study at a time, our total sample size should be divisible by 20. A sample size of 210 will provide 85% power to detect a difference of 1 on a 10 point scale with at standard deviation of 2.4 assuming a two-sample t-test with equal variance. The IMMPACT guidelines suggest that a change of 1 on the BPI is a minimum clinically significant difference. Additionally, the difference we found in our pilot trial was 1 (SD=2.4). Therefore, a sample size of 210 is sufficient to detect this effect size. To become divisible by 20 and allow for 25% dropout (slightly more than in the pilot trial) we will recruit 280 participants. With our anticipated sample size, we will be able to estimate a margin-of-error of 1.5 percentage points for 95% intervals. For secondary outcomes, we can detect an effect size of 0.4, a medium effect, for continuous measures and a difference of proportions between 7.5% and 17% for binary measures, each with 85% power.

Interim & Final Analyses. We will not have any planned interim looks for stopping for efficacy, although safety and tolerability data will be monitored by the study DSMB at each meeting. The final analyses will be conducted once study follow-up is complete, after all data is

cleaned, and once the study database is locked. We anticipate database lock will happen by February 2024 with completion of primary analyses occurring by March of the same year.

Analysis Sets. The full analysis set will be based on an intention-to-treat (ITT) analysis with a per-protocol (PP) sensitivity analyses. The ITT analysis set will comprise all participants who have been randomized to either study arm, regardless of length of follow-up or actual intervention received.

Endpoint and Covariates

Our primary outcome will be the Brief Pain Inventory (BPI)-Total score, a commonly used composite measure of pain severity and the impact of pain on an individual's function. The BPI asks 11 questions about pain severity (pain at its worst, least, average, and right now) and the interference of pain in several aspects of patients' lives (activity, mood, walking ability, work, relations with other people, sleep, and enjoyment of life) on a scale of 0 (no pain/does not interfere) to 10 (pain as bad as you imagine/completely interferes). The BPI-Total score is the average score across all 11 questions.

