There were no covariates included in our models, only time and treatment group indicator. We used linear mixed effects models which do not require adjustment for baseline as a fixed effect as it is included as an outcome. This allows for estimation of treatment effects at all follow-up times that takes into account any baseline differences between groups.

Handling of Missing Values. As a preventive measure, we will make every attempt to document all reasons for missing data. In addition, baseline characteristics will be compared between participants who do and do not withdraw from the study as a way to assess the impact of missing information and attrition. We will also compare the rates of lost-to-follow-up (LTF) between study arms.

Our general assumption will be that missing data is of the Missing at Random (MAR) mechanism. In this case, the use of linear mixed models for the primary analysis will be sufficient in reducing the impact that missing data has on biasing the primary results. Additionally, we will conduct a sensitivity analysis using multiple imputation via chained equations (MICE) to see how robust the overall inferences are.

Statistical Analyses.

The primary outcome – BPI-Total score – and the other secondary outcomes will be assessed as continuous variables. Linear mixed effects models will be performed to test differences between intervention and control conditions at the immediate post intervention and at 3 months. Models will include random effects for participant and therapy group. Therapy group is an identifier of the group of 20 that were randomized to create a STOMP group of 10. Fixed effects will be STOMP indicator, time and STOMP by time interaction. The primary hypothesis will be tested using the least squared means of each group at each time. We will check distributional

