assumptions for these models using residual analysis including studentized residuals for individual observations, PRESS residuals which are composite residuals across an individual in longitudinal analysis, and Cook's distance. In compiling our analysis set, we will use an Intention to Treat (ITT) approach. We chose ITT for two reasons: 1) it fully exploits the benefits of balancing through randomization by including all patients who are randomized in the analysis; 2) it is a more "real-world" assessment of the intervention's impact as it allows for incomplete adherence and includes participants who may unintentionally cross over from the control to the intervention condition. Each of these issues can be handled well within the linear mixed models that will allow investigators to plot model-predicted trajectories for individuals with incomplete data. An additional advantage of linear mixed models is that they do not assume that the time between assessments is fixed and data for individuals who miss a time point can still be included. However, as this is the first efficacy trial to investigate STOMP, we will also conduct a per-protocol/as treated sensitivity analysis to understand the impact of the intervention without these complicating factors and adjust for differences by site. As a sensitivity analysis, missing data will be examined using multiple imputation methods. Specifically, multiple imputation using chained equations will be performed using previous baseline outcome data. Data will be imputed separately for each treatment group to improve efficiency and reduce bias in the treatment effect estimate.¹ Response to treatment defined by a reduction of at least 30% BPI Total score will be compared between groups using generalized linear mixed models with binary outcome using the same model effects and random components as the primary analysis.

Reference

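### The undefined per-protocol/as-treated analysis selects on attendance in one arm only, so it cannot show STOMP's impact free of non-adherence and crossover

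*Combined protocol and SAP*

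**What the plan says.** The SAP refers to this analysis twice. Under Analysis Sets: "The full analysis set will be based on an intention-to-treat (ITT) analysis with a per-protocol (PP) sensitivity analyses". Under Statistical Analyses, ITT is preferred because it keeps the balance from randomisation and because "it allows for incomplete adherence and includes participants who may unintentionally cross over from the control to the intervention condition". Since this is the first efficacy trial of STOMP, the SAP then adds a "per-protocol/as treated sensitivity analysis to understand the impact of the intervention without these complicating factors" "and adjust for differences by site".

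Three other places bear on it:

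- SAP, Endpoint and Covariates: "There were no covariates included in our models, only time and treatment group indicator". Baseline BPI enters as one of the repeated outcomes.
- Protocol III d), Intervention: STOMP has 12 sessions, half group and half individual. Missed sessions are expected. Make-up and phone sessions are offered, and people unwilling to attend may be asked to complete assessments only.
- Protocol III e), Comparison Condition: controls get usual care and the manual, and "no additional treatment will be provided to participants allocated to the control group".

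Neither document gives a minimum number of sessions for adherence, a definition of crossover, or an expected attendance rate.

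**The concern.** Per-protocol and as-treated are different analyses. In the usual sense, the first excludes people who did not adhere and the second regroups people by what they received. Analysis Sets names one of them; Statistical Analyses joins the two with a slash. With no set defined, the choice can be made after the data are seen.

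Attendance happens after randomisation and may be related to prognosis. Only STOMP participants can be sorted by it, because controls have nothing comparable to attend. Either version therefore compares a selected part of one arm with an unselected comparator, or with a comparator that also contains the people who did not attend. Dilution from non-adherence is exchanged for possible confounding. Adjusting for site does not capture who attends within a site.

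What is at stake is the reading of a secondary result. The SAP says in advance that this estimate shows the intervention's impact without the complicating factors, and a reader would take it as the effect in those who received STOMP. The planned analysis cannot carry that meaning.

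**Working it through.** **The plan's own figures.** SAP, Sample Size Calculation: difference 1, SD 2.4, 85% power, N = 210, recruiting 280. Taking two-sided 5% (not stated in that section), n per arm = 2 × (1.960 + 1.036)² × 2.4² / 1² = 103.4, so 104 per arm or 208 in total, against 210. Power with 105 per arm is 85.5% (normal) or 85.2% (t). 210 / (1 − 0.25) = 280. The figures reproduce, so 105 observed per arm and SD 2.4 are used below.

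**Assumptions not in the documents.** True effect zero; a share c of the STOMP arm counts as attenders; attenders would score δ points better than non-attenders whatever the treatment; no control crossover; per-protocol drops non-attenders; as-treated moves them to the comparator; a simple two-group comparison at follow-up.

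**Bias.** Attenders lie δ(1 − c) above their arm's mean and non-attenders lie δc below it.

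- Per-protocol (attenders against all controls): δ(1 − c).
- As-treated (attenders against controls plus non-attenders): the comparator mean is lowered by δc(1 − c)/(2 − c), so the bias is δ(1 − c)[1 + c/(2 − c)] = 2δ(1 − c)/(2 − c).

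**False-positive rate.** With d = bias / SE and SE = 2.4 × √(1/n₁ + 1/n₂), the rate is Φ(d − 1.96) + Φ(−d − 1.96). Here n₁ = 105c, and n₂ = 105 (per-protocol) or 105(2 − c) (as-treated).

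Example, c = 0.6 and δ = 1.0, as-treated: bias = 2 × 0.4 / 1.4 = 0.57; n₁ = 63, n₂ = 147; SE = 0.361; d = 1.58; rate = 35%.

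| Attendance c | δ | Per-protocol bias (false positives) | As-treated bias (false positives) |
|---|---|---|---|
| 60% | 0.5 | 0.20 (8%) | 0.29 (12%) |
| 60% | 1.0 | 0.40 (18%) | 0.57 (35%) |
| 70% | 0.5 | 0.15 (7%) | 0.23 (10%) |
| 70% | 1.0 | 0.30 (13%) | 0.46 (26%) |
| 90% | 0.5 | 0.05 (5%) | 0.09 (6%) |
| 90% | 1.0 | 0.10 (6%) | 0.18 (8%) |

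**Cross-check with a second model.** Let attendance depend on a latent propensity correlated ρ with improvement that would happen anyway. At 70% attendance and ρ = 0.2, per-protocol bias is 0.24 points (10%) and as-treated bias 0.37 (18%). This matches the formulas above with δ = 0.8 (0.8 × 0.3 = 0.24; 0.8 × 0.6/1.3 = 0.37). In 10,000 simulated trials ITT stayed at bias 0.00 and 4.7%. With ρ = 0, neither version is biased.

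**Effect of the baseline.** If half of δ is already present at baseline and the contrast is on change, δ halves. At 70% attendance as-treated bias is then 0.12–0.23 points (6–10%) and per-protocol 0.08–0.15 (5.5–7%), keeping the same SE. If the whole gap is present at baseline, both biases are zero.

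**The case against.** The strongest reply is that nothing decisive rests on this analysis. It is labelled a sensitivity analysis, ITT is primary, and the SAP defends ITT on the ground that it keeps randomised balance. That stands. A reader might infer that the trial's main conclusion is at risk; the documents do not support this, and ITT shows no bias in the simulation above.

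A reader might also infer that the SAP commits to dropping non-attenders or moving them to control. It does not: the sets are undefined, and the contrasts computed here are the usual meanings of the two terms. The missing definition is part of the point.

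A third tempting reading is that the analysis will favour STOMP. The documents give neither an attendance rate nor any link between attendance and prognosis. If people in worse pain attend more, the bias runs against STOMP. The eligibility requirement to be able and willing to attend (Protocol III a), with make-up and phone sessions, may raise attendance and shrink the bias.

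The illustration is also cross-sectional, whereas the SAP models baseline BPI as an outcome with a STOMP-by-time interaction. A change contrast would remove baseline differences in level but not differences in prognosis for change. The SAP also says the hypothesis is tested on least squares means of each group at each time, so it is unclear which contrast applies. This limits the size of the bias but does not make the stated interpretation valid.

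Finally, a complier-average analysis rests on assumptions of its own, which are costed with the change below.

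**Conclusion.** The point holds as a limited one. The analysis is undefined, it would select on a post-randomisation variable in one arm, and the planned adjustment does not address that, so the interpretation the SAP attaches to it is not supported.

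The size is uncertain. Against a design difference of 1 point, the illustration runs from negligible (90% attendance, small prognostic gap) to more than half that difference (as-treated, 60% attendance, 1.0-point gap). It rests on assumed attendance, an assumed gap in one direction, no crossover and a follow-up-only contrast. It shows what the analysis could do, and is no forecast of what it will do. In the worked cases as-treated is always more biased than per-protocol, so leaving the choice open matters. This is a worthwhile improvement to a secondary analysis and no fault in the primary one.

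**What to change.** Before database lock:

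1. Pre-set an attendance threshold, kept low, and define crossover, meaning STOMP sessions received by a control participant.
2. Make the adherence analysis a complier-average effect by two-stage least squares: everyone stays in the randomised arm, and allocation is the instrument for attendance received in either arm.
3. Include baseline BPI, site and the two randomisation strata (long-term opioid therapy, chronic multisite pain). These must be listed, because the primary model has no covariates to carry over.
4. Use therapy-group-robust standard errors with a small-sample t reference. 280 / 20 = 14 groups, so about 13 degrees of freedom. In null simulation with 14 groups a normal cut-off rejected 6.8% and t(13) 4.8%.
5. Use the planned multiple imputation for missing outcomes, because plain two-stage least squares loses the mixed model's handling of data missing at random, and 25% dropout is planned for.
6. Report any per-protocol or as-treated table as non-randomised and descriptive, and delete the claim that it shows impact without the complicating factors.

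The method suits the design: both arms receive the manual, and attendance is already recorded on sign-in sheets and session forms. In a null simulation (70% attendance, attenders 0.8 points better anyway) it gave bias of about 0.01 and 5.0% rejection.

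The work is SAP wording and one extra analysis. The statistical price is a wider interval and an exclusion restriction: allocation must act only through attendance above the threshold. Partial attendance below it breaches this and inflates the estimate. For example, with an effect of 1.0 above the threshold, 0.4 below it and 70% above, the ITT effect is 0.7 × 1.0 + 0.3 × 0.4 = 0.82, and 0.82 / 0.7 = 1.17. Hence the low threshold.

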Comprehension will be assessed by asking the participant to summarize the study activities or some general open ended questions will be asked like what can you tell me about this study, can you tell me about how long the study may last, etc. The consent process is estimated to take around 30 minutes. Study staff will ensure that the participant has signed and dated the consent form including the HIPAA form. All signed consent forms will be stored in locked file cabinets under respective participant files.

Baseline Assessment

The research staff will then administer the baseline assessment which includes a confirmatory set of screening questions via RedCap. Confirmation of the participant's eligibility will be recorded in RedCap. If a participant is ineligible based on this RedCap assessment, they will be given a \$50 incentive and thanked for their time, and they will

not be considered to have been enrolled in the study at any point (informed consent is asked before this point so that we can use any data generated in published findings). If a participant is eligible, they will also be thanked for coming and given their \$50 incentive payment for their time. Completion of Baseline assessment will be recorded in excel logs.

RANDOMIZATION

Our team will utilize a 1:1 ratio for allocation to the STOMP intervention and Usual Care (UC) conditions. Our study statistician, [name], will use SAS to generate the randomization scheme stratified by whether the participant is on long-term opioid therapy (taking prescribed opioids for at least 3 months) and whether they have chronic multisite pain (pain in at least 3 locations or pain all over). Importantly, the PIs and outcomes assessors will be blinded to intervention vs. comparison allocation. Participants in the intervention and comparison conditions will have full access to all available clinical services at their respective sites.

d) INTERVENTION

The intervention group will receive “treatment as usual” plus the STOMP behavioral intervention. The “treatment as usual” refers to the standard of care that patients receive at the UAB and UNC clinics. This standard of care is for patients to discuss chronic pain with their providers at their discretion. Although highly variable, providers can recommend and prescribe pharmacologic (e.g., opioid and other pain medication), non-pharmacologic (e.g., physical therapy, referral to psychology) approaches for pain. This study will not interfere in any way with usual care.

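### The only missing-data sensitivity analysis keeps the missing-at-random assumption of the primary model, so it cannot show whether the result is robust to departures from that assumption

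*Combined protocol and SAP*

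**What the plan says.** The SAP, under Handling of Missing Values, states: "Our general assumption will be that missing data is of the Missing at Random (MAR) mechanism". It relies on the linear mixed model to limit bias under that assumption. It then adds multiple imputation by chained equations "to see how robust the overall inferences are".

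The SAP's Statistical Analyses section gives the detail: "multiple imputation using chained equations will be performed using previous baseline outcome data", run separately in each treatment group. No shift, reference-based rule, pattern-mixture model or other departure from MAR is described anywhere.

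Other planned steps bear on missing data:
- The SAP will record reasons for missing data, compare baseline characteristics of those who do and do not withdraw, and compare loss to follow-up between arms.
- A per-protocol/as-treated analysis addresses incomplete adherence and crossover.
- The protocol (Reminder calls) says that participants who no longer want sessions may be asked to continue with outcome assessments only.

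**The concern.** A sensitivity analysis for missing data is useful when it changes the assumption that cannot be checked from the observed data. Here that assumption is MAR. Chained-equations imputation with no shift keeps it. Imputing by arm lets the relation between visits differ by arm, but missing values are still predicted from the pattern seen in those who stayed.

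The risk is real in this design. The BPI is self-reported. The protocol (Randomization) blinds the investigators and outcome assessors, but participants know whether they attend sessions. Only the STOMP arm has the 12 sessions and the transit vouchers for them, so reasons for loss can differ between arms. If STOMP participants who do not improve are more likely to miss the assessment, both planned analyses err in the same direction. A positive result could then be called robust on evidence that did not test it.

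**Working it through.** **Inputs from the documents.** SAP, Sample Size Calculation: "A sample size of 210 will provide 85% power to detect a difference of 1 on a 10 point scale", SD 2.4, "assuming a two-sample t-test with equal variance", 25% dropout, 280 recruited. Protocol, Randomization: 1:1 allocation, so 140 per arm. The significance level is not stated; two-sided 0.05 is assumed.

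**The plan's own figures.**
- n per arm = 2 x (1.960 + 1.036)² x 2.4² / 1² = 103.4, so 104 per arm and 208 in total (SAP: 210).
- Power at 105 per arm is 85.5% by the normal formula and 85.2% by the noncentral t (SAP: 85%).
- 210 / 0.75 = 280.

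The figures reproduce. The allowance for 25% dropout is sound for power; what follows concerns bias.

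**Bias when MAR fails in STOMP.** Let m be the fraction of STOMP participants missing at the primary time point, and k the number of BPI points by which they are worse than MAR predicts. The effect over all randomised participants is then the MAR estimate minus m x k. At m = 0.25 and k = 1, an estimate of 1.0 corresponds to 1.0 - 0.25 = 0.75.

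**Shift at which significance is lost.** SE = 2.4 x sqrt(2/n), with n observed per arm. The smallest significant estimate is c = 1.96 x SE. The tipping shift is (estimate - c) / m. At 25% missing, SE = 2.4 x sqrt(2/105) = 0.331 and c = 0.649.

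| Missing | Observed per arm | c | Estimate 1.0 | Estimate 0.8 |
|---|---|---|---|---|
| 15% | 119 | 0.610 | 2.6 points | 1.3 points |
| 20% | 112 | 0.629 | 1.9 points | 0.9 points |
| 25% | 105 | 0.649 | 1.4 points | 0.6 points |
| 30% | 98 | 0.672 | 1.1 points | 0.4 points |

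A useful benchmark is that missing STOMP participants gained nothing, so that k equals the estimate. At 25% missing, an estimate of 1.0 falls to 0.75, still above 0.649. An estimate of 0.8 falls to 0.8 x 0.75 = 0.60, below it.

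**Can the planned check detect the problem?** A simulation used 140 per arm, about 25% missing at post-intervention and a true effect of 1.0. It assumed correlations of 0.5 between baseline and follow-up and 0.7 between post-intervention and 3 months. A likelihood analysis using all visits stood in for the mixed model; the imputation used baseline only. In the second pair of rows, STOMP participants with worse outcomes were more likely to be missing.

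| Missingness | Return at 3 months | Likelihood | Imputation |
|---|---|---|---|
| Completely at random | 0% | 1.00 | 1.00 |
| Completely at random | 40% | 1.00 | 1.00 |
| Related to outcome in STOMP | 0% | 1.40 | 1.40 |
| Related to outcome in STOMP | 40% | 1.34 | 1.41 |

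The two analyses agree exactly or nearly so, whether or not both are biased.

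**The case against.** The best defence is that the plan does more about missing data than the imputation alone. It tries to keep participants who stop sessions in follow-up, the protocol allows a 1-month window and assessment by phone, and dropout is described and compared by arm. All of this stands: leaving sessions is not the same as missing the outcome, and the descriptive checks may show that loss is uneven. They do not re-estimate the treatment effect, however. Nor does the per-protocol analysis, which is aimed at adherence.

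It is also fair that the SAP never says in so many words that the imputation assumes MAR. Standard chained equations with no stated shift do so.

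Some stronger readings are tempting, but the documents do not support them:
- A reader might infer that the imputation uses less information than the mixed model. The phrase about previous baseline outcome data is ambiguous; it may mean previous and baseline values. Even if it means baseline only, the loss in the simulation is trivial: the SD of the estimate is 0.323 against 0.317 with 40% returning at 3 months, and equal with none returning.
- A reader might infer that therapy group is left out of the imputation and that between-group variance is therefore understated. The SAP gives no full list of predictors, so this is inferred from silence, and its size has not been calculated.
- A reader might infer that agreement between the analyses is guaranteed. It is not: they gave 1.34 and 1.41 in one scenario. The point is that agreement is uninformative about MAR.
- A reader might infer that the trial cannot withstand 25% dropout. That figure is a planning allowance, and power for it is covered.

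**Conclusion.** The point holds in this form: no planned analysis departs from MAR, so the stated aim of checking robustness is not met for the assumption that matters most. The primary model itself is not at fault, and the documents do not show that MAR fails.

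The size depends on the scenario. At 25% missing, each point by which missing STOMP participants are worse than predicted means that the MAR estimate overstates the effect by 0.25. An estimate equal to the design difference of 1.0 tolerates a shift of about 1.4 points, and between 1.1 and 2.6 points over 30% to 15% missing. It would survive the case in which missing STOMP participants gained nothing. An estimate of 0.8 would not, with 25% missing.

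These figures assume two-sided 0.05, SD 2.4, equal missing fractions in both arms, a shift in STOMP only, an SE held at its MAR value and no therapy-group clustering. An equal shift in both arms with equal loss would cancel. The 1.4-point figure is one scenario and should not be read as a property of the trial.

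**What to change.** Keep the primary mixed model, and keep the by-arm imputation as the zero-shift case. Then change the SAP in two places.

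1. State the imputation model: baseline and all observed follow-up BPI values, with the stratification factors, site and therapy group where the model supports them. Sessions attended can be used in the STOMP arm only, because usual care has none.
2. Add a prespecified delta-adjusted tipping-point analysis of BPI-Total at the primary time point. Worsen the imputed STOMP values in steps, for example 0 to 2 points by 0.5, extended if the conclusion has not changed. Report the estimate and interval at each step and the shift at which the conclusion changes.

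The SAP puts the primary time point immediately after the intervention, while the protocol (Assessments) puts it at 3 months. The new text should name the one that is settled on.

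The cost is SAP wording and a few extra runs on data already collected. The imputation model becomes somewhat more complex: with 280 / 20 = 14 therapy groups and about 105 observed participants per arm, not every predictor may be estimable. The plausible range of shifts remains a judgement, but the display lets the reader see it and disagree.
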